2.3 Study Duration

Subjects will be confined for approximately 72 hours at the study site for the Surgical and Treatment Periods. The maximum study duration for each subject is approximately 6 weeks. This duration includes up to 28 days of Screening Period, 1 day (Day 0) of Surgical Period, up to 9 hours post-surgery, 48 hours of treatment and inpatient assessments, and 5 to 9 days after surgery of follow up or early withdrawal.

2.4 Study Treatments and treatment assignments

2.4.1 Treatment Groups

The three treatment groups to be evaluated in this trial are described in [Table 2-1](#) below

Table 2-1: Treatment Groups

Treatment group	Day 1						Day 2					
	Dose 1	Dose 2	Dose 3	Dose 4	Dose 5	Dose 6	Dose 1	Dose 2	Dose 3	Dose 4	Dose 5	Dose 6
100 µg	100 µg	100 µg	100 µg	100 µg	100 µg	100 µg	100 µg	100 µg	100 µg	100 µg	100 µg	100 µg
200 µg	200 µg	200 µg	200 µg	200 µg	200 µg	200 µg	200 µg	200 µg	200 µg	200 µg	200 µg	200 µg
Matching Placebo	P	P	P	P	P	P	P	P	P	P	P	P

2.4.2 Method of Treatment Assignment, Randomization Ratio, and Stratification

Subjects who have met all of the inclusion and none of the exclusion criteria, have provided written informed consent, and have experienced a pain intensity rating of ≥ 4 on the NRS during the 9-hour period after discontinuation of the anesthetic block are eligible to be enrolled in the study. They will be randomly assigned to 1 of 3 treatment groups: Fentanyl Sublingual Spray 100 µg q4h, 200 µg

q4h, or matching placebo. The randomization will be stratified by center and use mixed blocks with a 1:1:1 ratio to ensure even distribution of subjects across each treatment group in every site.

In addition, an enrollment anticipated at each of the sites in the following:

- [REDACTED] (PI: Dr. [REDACTED]) = approximately 30 subjects
- [REDACTED] (PI: Dr. [REDACTED]) = approximately 15 subjects

The actual randomization assignment will be made through an Interactive Web Based System (IWRS) called [REDACTED]. [REDACTED] is a Secure Socket Layer (SSL) web portal that allows 24/7 access to clinical trial information. Authorization is based on approved access control list (ACL) that determines a user's access to the site. The [REDACTED], who is not otherwise involved with the study, is responsible for the implementation and maintenance of [REDACTED]. Each user will be trained in how to use the website. A [REDACTED] user manual will be supplied to all study personnel with instructions on using the website.

The Randomization/Supply module of [REDACTED] allows authorized users to request randomization (Site Personnel only) into the trial. The detailed description and instructions are included in the [REDACTED] user manual. [REDACTED] has further documentation and validation of [REDACTED] specifically with regards to preserving the blinding of this study.

2.5 Blinding

As this is a double-blind trial, all subjects and study personnel involved in the conduct of the study, including data management, will be blinded to treatment assignment.

2.5.1 Maintenance of Blinding

The randomization lists containing the assignment of subjects to treatment groups will be securely provided to the person involved in randomizing the subjects (i.e. the WebMaster), who has no role in screening, enrolling, qualifying, or evaluating study subjects. No other study personnel other than the WebMaster and the randomization code generator will have access to the randomization codes for the study.

2.5.2 Time to Un-blinding

Treatment un-blinding and release of the randomization codes of the investigational product (IP) assignments for the study will only occur 1) due to emergency un-blinding because of safety reasons or 2) at the time of database lock when all randomized subjects have completed the study or discontinued from the study and after all clinical data have been received and data inconsistencies have been resolved.

3. STUDY ASSESSMENTS/ ENDPOINTS

3.1 Efficacy Endpoints

3.1.1 Primary Efficacy Endpoint

The primary efficacy endpoint is the NRS summed pain intensity difference (NRS SPID) (calculated as a time weighted average) over 0 to 48 hours (NRS SPID-48) after Time 0.

3.1.2 Secondary Efficacy Endpoints:

The secondary endpoints are the following:

- NRS SPID over 0 to 24 hours (NRS SPID-24), over 0 to 8 hours (NRS SPID-8), and over 0 to hours (NRS SPID-4) after Time 0
- Total pain relief (TOTPAR) over 0 to 48 hours (TOTPAR-48), over 0 to 24 hours (TOTPAR-24), over 0 to 8 hours (TOTPAR-8), and over 0 to 4 hours (TOTPAR-4) after Time 0
- Subject's global evaluation of study drug
- Time to onset of analgesia (measured as time to perceptible pain relief confirmed by meaningful pain relief using the 2-stopwatch method)
- Pain relief score on a 5-point categorical scale at each scheduled time point after Time 0
- Peak pain relief
- Time to peak pain relief
- Time to first perceptible pain relief

- Time to meaningful pain relief
- Proportion of subjects using rescue medication
- Time to first use of rescue medication (duration of analgesia) following each dose of IP
- Total use of rescue analgesia over 0 to 24 hours and over 0 to 48 hours
- NRS pain intensity difference (NRS PID) at each scheduled time point after Time 0
- NRS pain intensity score at each scheduled time point

3.2 Safety Assessments

Safety assessments will include the evaluation of AEs, physical and oral examinations, vital sign measurements, pulse oximetry, and 12-lead ECGs. Clinical laboratory tests will be performed at Screening only.

The safety endpoints are the incidence of treatment-emergent adverse events (TEAEs), physical and oral examination findings, and changes in vital signs, pulse oximetry, and ECG measurements.

4. SAMPLE SIZE DETERMINATION AND RATIONALE, STATISTICAL POWER, AND SIGNIFICANCE LEVEL

A total of 45 subjects are planned to be enrolled for the study. A sample size of 15 subjects per treatment group will provide $\geq 80\%$ power to detect a minimal standardized effect size of 0.5 between the 100 μg q4h, 200 μg q4h active treatment arms, and placebo in NRS SPID-48 using a 3-group analysis of covariance (ANCOVA) with baseline NRS score as the covariate with a 0.05 two-sided significance level (EAST v6).

5. INTERIM ANALYSIS

No Interim Analysis is planned for this study.

6. ANALYSIS POPULATIONS

6.1 Intent-to-Treat (ITT) population

The intent to treat (ITT) population will consist of all subjects who are randomized. The ITT

population is the primary population for the efficacy analysis.

6.2 Per Protocol (PP) Population

The per protocol (PP) population will consist of all ITT subjects who receive at least 1 dose of study drug, who remain in the study for at least 48 hours of treatment, and who do not incur a major protocol violation that would challenge the validity of their data. This population will be used to evaluate the sensitivity of the primary efficacy analysis.

6.3 Safety Population

The safety population will include all subjects who are treated with at least one study drug. The safety population is the population for all safety assessments.

7. DATA CONVENTION AND RELATED DEFINITIONS

7.1 Baseline Definition

For all parameters, baseline will be defined as the last available value before the randomized treatment administration.

7.2 Duplicate Data

For unplanned duplicate data within a protocol-specified visit, the last measured value will be used for the analysis. If it is not possible to identify the “last measured value” the average of the duplicate values will be used.

No data will be excluded. All collected data will be listed.

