3.3. Removal of Subjects from Therapy or Assessment

All subjects will be advised that they are free to withdraw from participation in this study at any time, for any reason, and without prejudice. Every reasonable attempt should be made by the investigator to keep subjects in the study. However, subjects must be withdrawn from the study if they withdraw consent to participate. Investigators must attempt to contact subjects who fail to attend scheduled visits by telephone or other means to exclude the possibility of an AE being the cause of withdrawal. Should this be the cause, the AE must be documented, reported, and followed as described in Section 6.2.6.8. The sponsor reserves the right to request the withdrawal of a subject due to protocol violations or other reasons.

The investigator also has the right to withdraw subjects from the study at any time for lack of therapeutic effect that is intolerable or otherwise unacceptable to the subject, for intolerable or unacceptable AEs, intercurrent illness, noncompliance with study procedures, administrative reasons, or in the investigator's opinion, to protect the subject's best interest.

If one of the following events occur during the Treatment Period, the subject will be discontinued from further study participation:

1. Hypoxia with oxygen saturation $\leq 90\%$ on repeat measurements over 3 minutes, despite stimulation and receiving oxygen 2-4 L/min via nasal cannula.
2. Hypoxia or respiratory depression requiring the use of naloxone for reversal.
3. Need for noninvasive respiratory maneuvers (eg, jaw thrust, bag-valve mask for positive pressure ventilation, etc.) to improve or maintain adequate respiratory status (ventilation and/or adequate oxygen saturation) at any point during the study.
4. Hypotension requiring intervention, as follows:
 - a. If asymptomatic and <80 mm Hg systolic blood pressure on 3 successive repeat measurements over a 15-minute period.

- b. If symptomatic, but >80 mm Hg systolic blood pressure and does not respond to conservative measures such as oral hydration and/or no more than 1 liter of IV fluids (if more than 1 liter of IV fluid is needed and/or if naloxone is administered, the subject will be discontinued from further dosing).

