Oxygen saturation will be monitored continuously and the study team will measure all vital signs (blood pressure, heart rate, respiratory rate, and oxygen saturation) at least every 5 minutes until the AE of hypotension or hypoxia as described above is no longer present.

5. If >8 mg i.v. ondansetron is needed within an 8-hour segment and persistent nausea and/or emesis is present.
6. Pain cannot be adequately managed (in the investigator's opinion) by a combination of study drug and rescue medication, or who develop unacceptable side effects during the study, will be discontinued from further study participation.

Pain will be managed according to usual standard of care at the investigator's discretion.

If a subject is withdrawn before completing the study, the reason for withdrawal and the date of discontinuation will be recorded on the appropriate case report form (CRF). Whenever possible and reasonable, the evaluations that were to be conducted at the completion of the study should be performed at the time of premature discontinuation.

If a subject discontinues the study prematurely, pain intensity, pain relief, and the subject's global satisfaction with study treatment should be assessed and recorded immediately before discontinuation.

Withdrawn subjects will not be replaced. If a substantial number of subjects are withdrawn from the study, then the sponsor will evaluate the need for developing replacement criteria.

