APPENDIX 3. HYPOXIA ASSESSMENT (PROPOSED GUIDANCE)

Hypoxia Level	Condition	Action
1	Hypoxia on Room Air	
 • Verbal Stimulation/Position Change. • If not able to maintain a saturation of greater than 90% after two verbal interventions, then advance to Level 2.
2	Hypoxia on Oxygen via Nasal Cannula	
 • Administer oxygen 2-4 L/min via nasal cannula. • If not able to maintain a saturation greater than 90% despite oxygen via NC, then advance to Level 3.
3	Hypoxia on Oxygen via Face Mask	
 • Change oxygen to facemask delivery. • If not able to maintain a saturation greater than 90% despite oxygen via FM, then advance to Level 4.
4	Hypoxia despite Maximal Oxygen Therapy	Mechanical Intervention (sternal rub, airway management) + Chemical Narcotic Reversal

Note: Proposed process for Hypoxia is a guidance, and will not supersede the investigator's medical judgement and treatment process. If oxygen is administered, the oxygen treatment should be documented as a concomitant medication.

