8.2.9 Vital Signs

Tabulations of raw data and change from baseline values will be presented by time point for each vital sign parameter [*i.e.*, heart rate (beats/min), respiratory rate, oral body temperature ($^{\circ}\text{C}$ / $^{\circ}\text{F}$), systolic BP (mmHg), diastolic BP (mmHg), pulse oximetry (%)].

Summary will include the number of observations, mean, standard deviation, median, and minimum and maximum values. For change from baseline summaries, subjects with an undefined change from baseline, because of missing data, will be excluded.

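### SAP 7.2's last-reading rule has no exemption for safety data, so the SAP 8.2.9 tables can show a recovered value when hypoxia or hypotension coincides with a scheduled vital-sign or SpO2 reading

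*SAP*

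**What the plan says.** SAP 7.2 is a general data convention: "For unplanned duplicate data within a protocol-specified visit, the last measured value will be used for the analysis". If the last value cannot be identified, "the average of the duplicate values will be used". It then adds: "No data will be excluded. All collected data will be listed". It makes no distinction between efficacy and safety data.

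Protocol 3.3 lists the hypoxia and hypotension events that lead to discontinuation. During such an event the team repeats SpO2, respiratory rate, heart rate and blood pressure, with this frequency: "at least every 5 minutes until the AE of hypotension or hypoxia as described above is no longer present". These repeats are triggered by the event and do not appear in the schedule of assessments.

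SAP 8.2.9 says: "Tabulations of raw data and change from baseline values will be presented by time point for each vital sign parameter". Its parameter list includes systolic and diastolic pressure, heart rate, respiratory rate and pulse oximetry. The statistics are n, mean, SD, median, minimum and maximum. There is no worst-value summary and no count beyond a threshold.

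Protocol 8.2 and SAP 3.2 both name changes in vital signs and pulse oximetry as safety endpoints.

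**The concern.** Repeats of SpO2 and blood pressure are not random re-measurements here. They are taken because a reading was bad, and the protocol ends the series when the event has gone. A rule that keeps the last reading of such a series therefore leans towards the recovered value. The averaging fallback also dilutes the low readings.

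The table affected is the only planned by-arm summary of these endpoints. If episodes are more frequent on fentanyl than on placebo, the rule trims the active arms more, and the distortion runs towards no drug effect. The minimum and the threshold crossing, which matter most in an opioid safety summary, are the figures most exposed.

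**Working it through.** The plan gives no figure on this point, so there is none to reproduce. The check traces the rule through the documents and then applies it to assumed readings.

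**Does the rule reach these data?**
- SAP 7.2 covers unplanned duplicates within a visit. The event-driven repeats are off schedule, so the natural reading includes them.
- SAP 8.2.3 rules out imputation for safety data. Choosing among measured duplicates is not imputation, so this gives no exemption.
- If the repeats were instead held to be planned, because protocol 3.3 prescribes them, SAP 7.2 would not apply. The SAP would then have no rule for choosing the tabulated value.
- Protocol Table 2 allows ±10 minutes around scheduled SpO2 readings and the post-dose and 48-hour vital signs. At 5-minute steps, a series starting at −10 minutes has five readings in the window (−10, −5, 0, 5, 10); one starting at the nominal time has three (0, 5, 10). The SAP does not say whether later repeats are cut off.

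**Illustration: one arm, one time point.** The arm size of 15 is from SAP section 4. All readings are assumptions.
- SpO2: 14 subjects read 96 to 98%, sum 1358. One subject reads 88, 89, 90, 93, 97 at 5-minute steps.
- Systolic pressure: 14 subjects read 110 to 130 mmHg, sum 1698. One subject reads 78, 76, 79, 95, 112.
- Arm mean = (sum of the 14 + value used for the affected subject)/15.

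| Value used for the affected subject | SpO2 mean | SpO2 min | n ≤90% | SBP mean | SBP min | n <80 |
|---|---|---|---|---|---|---|
| First (88; 78) | 1446/15 = 96.40 | 88 | 1 | 1776/15 = 118.40 | 78 | 1 |
| Lowest (88; 76) | 96.40 | 88 | 1 | 1774/15 = 118.27 | 76 | 1 |
| Last, SAP 7.2 (97; 112) | 1455/15 = 97.00 | 96 | 0 | 1810/15 = 120.67 | 110 | 0 |
| Average, SAP 7.2 fallback (91.4; 88) | 1449.4/15 = 96.63 | 91.4 | 0 | 1786/15 = 119.07 | 88 | 0 |
| Last, if series starts at nominal time and is cut at +10 min (90; 79) | 1448/15 = 96.53 | 90 | 1 | 1777/15 = 118.47 | 79 | 1 |

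Baseline is untouched, so the mean change from baseline moves by the same amount as the mean. Last against first, that is (97 − 88)/15 = 0.60 points for SpO2 and (112 − 78)/15 = 2.27 mmHg for systolic pressure. The SD falls from 2.44 to 0.76 for SpO2 and from 12.30 to 5.68 for systolic pressure.

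**Range for SpO2.** Assume a low reading of 80 to 90% and a recovered reading of 95 to 98%. Each affected subject then moves the mean of 15 by (95 − 90)/15 = 0.33 to (98 − 80)/15 = 1.20 points. Three affected subjects in one arm move it by 1.0 to 3.6 points.

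The table's last row shows that the result depends on how repeats are assigned to the time point. If the series is cut while the episode continues, the low value survives.

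**The case against.** The strongest case against has five parts.

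1. **The episode is not lost.** Protocol 3.3 itself treats these events as adverse events. SAP 8.2.4 tabulates adverse events by arm, severity and relationship, and separately those leading to discontinuation. SAP 8.1.1 summarises reasons for discontinuation, and the listings keep every reading. A reader might infer that the signal disappears from the safety report; the documents do not support that. What remains is that these outputs do not give the depth of a desaturation or pressure fall by arm. The documents also set no SpO2 or pressure value at which a reading must be recorded as an adverse event.

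2. **The last reading need not be recovered.** The hypoxia criterion requires low saturation "on repeat measurements over 3 minutes, despite stimulation and receiving oxygen 2-4 L/min via nasal cannula", and the asymptomatic hypotension criterion needs three repeats over 15 minutes. Low values can therefore persist to the end of the window. This stands: the lean towards recovery is a tendency. A dip that recovers promptly on oxygen does not meet that hypoxia criterion. It falls under Appendix 3, which is proposed guidance and sets no recording interval.

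3. **The rule says unplanned duplicates, not any repeats.** This also stands. The documents do not show that the 5-minute readings would be entered under a scheduled time point.

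4. **Exposure is narrow.** SpO2 is recorded at only four scheduled post-dose times (90 minutes and 12, 24 and 48 hours). Episodes at other times miss the time-point table under any duplicate rule. This limits what a change to SAP 7.2 alone can achieve, and is a reason to add a summary that uses all recorded readings.

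5. **Safety is descriptive only.** True, but a descriptive table of a named endpoint should still not favour the better reading.

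**Conclusion.** The point holds in a limited form. As written, SAP 7.2 can replace a low post-dose reading with a later and often better one in the SAP 8.2.9 vital-sign and SpO2 tables, and nothing else in the plan restores the depth of the episode by arm. It requires that:
- an episode coincides with a scheduled reading;
- the repeats are entered under that visit;
- they count as unplanned duplicates.

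In the illustration, one such subject of 15 shifts the mean by 0.60 SpO2 points or 2.27 mmHg, raises the tabulated minimum from 88% to 96% or from 78 to 110 mmHg, and takes the threshold count from 1 to 0. Those figures rest wholly on assumed readings, and the documents give no expected frequency of episodes.

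A reader might go further and infer that the arms will look alike when they are not. That is not shown: few subjects may be affected, and the difference between arms is distorted only if episodes are unequally distributed. The primary efficacy result is not affected. The correction is nonetheless worth making before database lock, because the endpoints are named, the distortion favours better readings and the remedy is cheap.

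**What to change.** In SAP 7.2, state that neither the last-value rule nor the averaging fallback applies to post-dose vital signs and SpO2, and that the first (scheduled) reading is tabulated at each time point. Keep the rule for all other data, so that efficacy duplicates are still covered.

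In SAP 8.2.9, add by arm:
- the worst post-baseline value of each parameter;
- the number of subjects with any recorded SpO2 ≤90%;
- the number with any recorded systolic pressure <80 mmHg.

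These summaries should use all recorded readings, scheduled and unscheduled. Both figures already stand in protocol 3.3 and serve here only as reporting cut-offs. Protocol 8.5.4.4 already plans counts of this kind for the ECG.

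The cost is SAP wording and one short table. The safety figures may look slightly less favourable. Worst values partly reflect how often a subject was measured, so they should supplement the scheduled reading rather than replace it, with a footnote saying so.

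A flag for SpO2 readings taken on oxygen would help interpretation but should not be promised. Appendix 3 says only "If oxygen is administered, the oxygen treatment should be documented as a concomitant medication", and the SAP's concomitant-medication conventions work on dates, so the necessary start and stop times may not be available.

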7.3 Handling of Missing Data

7.3.1 Handling of Missing Data for Efficacy Assessments

Use of Rescue Medication: Any pain intensity or pain relief score occurring within 4 hours after a subject has taken rescue medication for pain will be replaced by the last pain intensity or pain relief score prior to that use of rescue medication. If a second rescue medication for pain is used within that 4 hour duration, the pain intensity or pain relief scores from the time of the first rescue medication will be replaced by the assessment prior to the second rescue medication for the next 4

hours. The same method will be employed for a third and subsequent rescue medication.

Missing due to Dropouts: Missing values for pain intensity after a subject drops out of the study will be imputed as follows in the primary analysis:

- For SPID endpoints, the last available SPID (truncated SPID) will be used for analysis (e.g., if a subject dropped out after 32 hours of initiation of treatment, the truncated SPID calculated using timepoints up to 32 hours will be used as the post 32 hour timepoints like 40 hours and 48 hours).
- For TOTPAR endpoints, the last available TOTPAR (truncated TOTPAR) will be used for analysis
- For PID endpoints, the last available pain intensity will be used to impute the missing pain intensity and to calculate the PID

In addition, a sensitivity analysis using 1) missing as missing (i.e., no imputation) for dropouts and 2) multiple imputation will be performed for the primary endpoint to explore the impact of missing data after a subject drops out. The details of the sensitivity analysis are described in [Section 7.4](#).

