7.4 Sensitivity Analyses

A sensitivity of the primary analysis using multiple imputation for missing data will be performed for the primary endpoint to assess the impact of missing data after subject's have dropped out. For the primary endpoint the following two sensitivity analyses will be conducted:

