7.4.1 Missing as Missing

The primary endpoint analysis will be conducted without any imputation.

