7.9.7 Summed Pain Intensity Difference (SPID)

The summed pain intensity difference (SPID) is to be calculated by multiplying the PID score at each post dose time point by the duration (in hours) since the preceding time point and then summing the values over the relevant time period.

$$SPID-48 = \sum_{i=1}^{21} (T_i - T_{(i-1)}) * PID_i$$

$$SPID-24 = \sum_{i=1}^{18} (T_i - T_{(i-1)}) * PID_i$$

$$SPID-8 = \sum_{i=1}^{14} (T_i - T_{(i-1)}) * PID_i$$

$$SPID-4 = \sum_{i=1}^{10} (T_i - T_{(i-1)}) * PID_i$$

Where $T_0 = 0$, T_i is the actual time, and PID_i is the PID score at time T_i .

The durations between nominal time points will be calculated using the actual times of the pain score measurement. If the actual time is missing the nominal planned time will be used.

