8.2 Analysis of Efficacy Data

8.2.1 Primary Endpoint

The primary efficacy endpoint is the NRS summed pain intensity difference over 0 to 48 hours after Time 0 (NRS SPID-48). The formula for SPID-48 calculation is presented in [Section 7.9.7](#). The primary variable will be analyzed using an analysis of covariance (ANCOVA) model, which will include treatment and site as main effects and baseline pain intensity as the covariate. The least square (LS) mean, standard error (SE) and 95% confidence interval (CI) for each treatment group will be estimated. In addition, the mean (LS mean) difference between each treatment and placebo, SE, p-value and the associated 95% CI will also be computed. Descriptive summaries (including mean, SD, median, minimum and maximum) will also be presented by treatment group. Missing values for pain intensity will NOT be imputed in the primary analysis.

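### SAP 7.3.1 imputes dropouts in the primary SPID-48 analysis, SAP 8.2.1 rules imputation out, and no text says which governs

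*SAP*

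**What the plan says.** SAP 7.3.1 gives a dropout rule for the primary analysis: "Missing values for pain intensity after a subject drops out of the study will be imputed as follows in the primary analysis". The rule for SPID endpoints is the truncated SPID, with a worked example of a subject who leaves after 32 hours. The same section then adds, with regard to SPID-48, that "a sensitivity analysis using 1) missing as missing (i.e., no imputation) for dropouts and 2) multiple imputation will be performed".

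SAP 8.2.1 specifies the primary model (treatment and site as main effects, baseline pain intensity as covariate) and closes with: "Missing values for pain intensity will NOT be imputed in the primary analysis". The sentence is not limited to isolated gaps and does not refer back to 7.3.1.

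SAP 7.4 announces the sensitivity work: "For the primary endpoint the following two sensitivity analyses will be conducted". The first of the two, 7.4.1, reads in full: "The primary endpoint analysis will be conducted without any imputation". The second, 7.4.2, is multiple imputation.

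The primary efficacy population is ITT (SAP 6.1): "The intent to treat (ITT) population will consist of all subjects who are randomized". The per-protocol set (SAP 6.2) is limited to subjects "who remain in the study for at least 48 hours of treatment".

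The protocol gives no missing-data rule for the primary analysis. Its section 8.5.3.3 leaves the specifics of the sensitivity analyses to the SAP. SAP section 11 describes the document as a first version, so no later text settles the matter.

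**The concern.** The two sections give opposite instructions for the same variable in the same analysis. A programmer working from 8.2.1 and one working from 7.3.1 could produce different primary results, and both could cite the SAP.

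Dropout is unlikely to be unrelated to outcome. Protocol 3.3 requires discontinuation when pain cannot be adequately managed with study drug and rescue, and for several safety events. Withdrawn subjects are not replaced, although the sponsor will consider replacement criteria if a substantial number withdraw. With 15 per arm, 2 or 3 dropouts are 2/15 = 13% to 3/15 = 20% of an arm.

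The sensitivity analyses are also affected. If the primary makes no imputation, 7.4.1 handles dropouts as the primary does and no longer tests that choice.

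**Working it through.** **Step 1: do the passages agree?** 7.3.1 says post-dropout pain intensity is imputed in the primary analysis. 8.2.1 says missing pain intensity is not imputed in it. Listing no imputation as a sensitivity analysis (7.3.1, 7.4.1) makes sense only if the primary does something else, which points to 7.3.1. So does the all-randomized ITT set. Neither is a statement of precedence.

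**Step 2: what could 8.2.1 mean in practice?**
- *Exclusion.* SPID-48 is missing for a dropout, who leaves the model. The primary is then not on all randomized subjects and 7.4.1 duplicates it. The per-protocol set omits the same subjects, so only 7.4.2 keeps them.
- *Sum of observed terms.* The result equals the truncated SPID. The primary number does not change, and 7.4.1 read the same way adds nothing.

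**Step 3: what truncation does.** SAP 7.9.7 computes SPID by "multiplying the PID score at each post dose time point by the duration (in hours) since the preceding time point" and summing. Stopping the sum at dropout is the same as setting PID = 0 for every later hour. Example: with a constant 3-point reduction and dropout at 32 h, the truncated SPID is 3 × 32 = 96, against 3 × 48 = 144 for the full period.

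**Step 4: size if 8.2.1 means exclusion.** The plan gives no figure to reproduce on this point.
- From the documents: 15 per arm (SAP 4), SD 100 (Protocol synopsis), two-sided 0.05.
- Assumed: true difference 50 (0.5 × 100, read as a pairwise difference), both doses equal, constant PID within a subject, improvement counted as positive, no covariates, placebo mean m from 0 to 144, and the dropout numbers and times.

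*Dropouts who resemble completers.* Exclusion gives 50 on average. With k dropouts at hour t, truncation lowers an arm mean by (k/15) × mean × (1 − t/48). For k = 3 and t = 8 this is (3/15) × (40/48) = 1/6 of the mean.

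| 3 dropouts at 8 h | Truncated difference | m = 0 | m = 96 | m = 144 |
|---|---|---|---|---|
| Active only | 50 − (m + 50)/6 | 41.7 | 25.7 | 17.7 |
| Placebo only | 50 + m/6 | 50.0 | 66.0 | 74.0 |
| Every arm | 50 × 5/6 | 41.7 | 41.7 | 41.7 |

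In simulation (40,000 trials per case, variance pooled over three arms, one active arm against placebo), the two rules disagreed on significance in favour of active as follows at m = 96: 16% (active only), 19% (placebo only) and 5% (every arm). With the F-test gate of Protocol 8.5.3.1 these become 12%, 18% and 5%. Without the gate, over m = 0 to 144, the range is about 4% to 26% for one-arm dropout and about 2.5% to 10% for dropout in every arm.

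*Dropouts with least relief.* Let the 3 placebo subjects with the lowest SPID-48 of 15 leave, with m = 96 and no active dropouts. The three lowest of 15 normal values average 1.31 SD below the mean, so their mean is 96 − 131 = −35.
- Exclusion: the other 12 average 3 × 131/12 = 32.8 above m, so the difference is 50 − 32.8 = 17.2.
- Truncation at 8 h: the placebo mean rises by (3/15) × 35 × (40/48) = 5.8, so the difference is 44.2.
- Truncation at 24 h: it rises by (3/15) × 35 × (24/48) = 3.5, so the difference is 46.5.

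A separate simulation run gave 44.0 and 46.3 under truncation and 17.1 under exclusion.

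*No dropouts.* The rules give the same result.

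**The case against.** The strongest reply is that the sections can be reconciled. The SPID rule in 7.3.1 fills in no pain score; it stops the sum. Only the separate rule for PID endpoints carries a pain score forward. A truncated sum could therefore satisfy 8.2.1 to the letter, and 7.3.1 is the more specific text on dropouts. This fails on 7.3.1's own wording, which introduces truncation as imputing missing pain intensity in the primary analysis. If the reply were accepted, 7.4.1 read the same way would repeat the primary, so the text would still need correcting.

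Two parts of the other side stand. All the numerical harm comes from the exclusion reading, which the SAP's structure disfavours. The size also depends on an undocumented placebo mean and on who drops out, so it can only be given as an illustrative range.

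A reader might infer that the planned primary analysis drops randomized subjects, or that its result will be wrong. The documents do not support that: they do not say that 8.2.1 means exclusion, and they give no dropout rate. Nor do the figures show one rule to be better in general. Exclusion returns the true 50 when dropouts resemble completers, and falls well below it when the least-relieved placebo subjects leave.

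**Conclusion.** The concern holds as a contradiction in the rule for the primary endpoint: wrong as written, with 7.3.1 the likelier intention. The textual finding needs no assumption.

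The consequence depends on the reading. If 8.2.1 means the sum of observed terms, the primary number is unaffected and the loss is an empty sensitivity analysis. If it means exclusion, the primary departs from ITT, and three dropouts in one arm can move the estimated difference by tens of SPID units in either direction. That size rests on the assumptions in the working, above all a true difference of 50 and the chosen dropout patterns; it is not a forecast. Because this is the primary analysis and the correction is cheap, it should be made before the SAP is finalized. Protocol 8.5 and 8.5.3.2 place that before database lock and unblinding.

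**What to change.** 1. Replace the last sentence of SAP 8.2.1 with: *Values missing after dropout are handled as in Section 7.3.1; intermittently missing scores before dropout are not imputed, and each interval in the 7.9.7 sum runs from the preceding observed time point.* The second clause is needed because the present sentence is the only one that covers isolated gaps: 7.3.1 deals with rescue and dropout only, and 7.9.7 deals with missing times, not missing scores.
2. Define SAP 7.4.1 as setting SPID-48 to missing for dropouts, so that the subject is excluded, with the rescue replacement of 7.3.1 kept. It then differs from the primary. Keep 7.4.2.
3. Optional: note in 7.3.1 that truncation is equivalent to PID = 0 after dropout.

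The cost is SAP wording and minor programming, with no protocol amendment and no new data.
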